## 5. Specific Aims:

**Aim #1:** to test the effect of an 8-session telephone and online problem-solving intervention on stroke caregiver's depressive symptoms at 1 and 12 weeks post-intervention.

**Aim #2:** to test the effect of the intervention on stroke caregivers' burden, self-efficacy, and health-related quality of life (HRQOL) at 1 and 12 weeks post-intervention.

**Aim #3:** to test the effect of the intervention on Veterans' outcomes: Functional abilities and healthcare utilization (i.e., unintended hospital bed days of care, number of emergency room visits, number of unscheduled clinic visits) at 1 and 12 weeks post-intervention.

**Aim #4:** to determine the intervention's budgetary impact.

**Aim #5:** Determine the acceptability of the intervention and the facilitators and barriers that Spanish-speaking stroke caregivers perceive when participating in the study.

We will conduct a two-group randomized controlled trial with repeated measures (baseline, 1 week post-intervention and 12 weeks post-intervention) and use mixed methods to determine caregivers' perceptions of the value, facilitators, and barriers to participating in the intervention. We will enroll 227 caregivers of Veterans with strokes. The caregivers will be recruited from the VACHS in San Juan, Puerto Rico, the James A. Haley Veteran's Hospital in Tampa, FL, and the Orlando VA Medical Center (VAMC) in Orlando, FL. Eligible caregivers

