## 6. Research Plan:

### Research Design and Methods Overview (Aims # 1, 2, 3).

Aim #1: (Primary Aim): to test the effect of an online and telephone support/Internet intervention on Spanish-speaking stroke caregiver's depressive symptoms at 1 and 12 weeks post-intervention.

Aim #2: to test the effect of the intervention on stroke caregivers' burden, self-efficacy, and health-related quality of life (HRQOL) at 1 and 12 weeks post-intervention.

Aim #3: to test the effect of the intervention on Veterans' outcomes: Functional abilities and healthcare utilization (i.e., unintended hospital bed days of care, number of emergency room visits, number of unscheduled clinic visits) at 1 and 12 weeks post-intervention.

Design: We will conduct a two-arm (intervention vs standard care), randomized controlled clinical trial (RCT) with three assessment points (baseline, 1 week post-intervention and 12 weeks post-intervention).

Study Location: Study participants will be recruited from the VA Caribbean Healthcare System (VACHS) in San Juan, Puerto Rico, James A. Haley Veteran's Hospital in Tampa, FL, and the Orlando VA Medical Center (VAMC) in Orlando, FL, but all study procedures will be conducted over the phone from either the North/Florida South Georgia Veterans Healthcare System (NF/SG VHS) in Gainesville, FL or the VACHS in San Juan. The James A. Haley and Orlando VAMC sites serve only as identification and referral sites.

Sample: The sample will consist of 227 Hispanic caregivers of Veterans with strokes, 21 years old or older who will be randomized to one of two study arms. In addition, we will conduct chart reviews on the 227 corresponding Veterans.

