criteria and who are still willing to participate after completing the baseline assessment will be randomized to the intervention group or standard care group. All participants will complete two post-tests; post 1 will occur at approximately 9-10 weeks after enrollment (or 1-2 weeks after completion of the intervention for participants in the intervention group), and post 2 will occur approximately 12-13 weeks after post-test 1. The post-test assessments will include the same tools used in the baseline data collection. In addition, at both post-tests we will ask caregivers to disclose any resources they may have used during the duration of the study. At the 12 week post-test assessment the data collector will also ask questions on the Bakas “Enactment” tool to obtain data concerning the caregivers’ perceptions of the intervention. The data collector, who will be blinded to the group assignment of the caregivers, will telephone the caregivers to obtain the post-test assessments. We will obtain data on healthcare utilization since baseline assessment from the MCAS the Decision Support System National Data Extracts (DSS NDE) and the Non-VA Medical Carefee-basis files. Team members abstracting data from CPRS will be trained and inter-rater reliability testing will be conducted for all data collectors. We will conduct the assessments and intervention sessions at times that are convenient to the caregivers. All caregivers will receive reimbursement for their participation in the study.

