### Intervention

Participants in the intervention group will participate in 8 weekly telephone sessions with an interventionist. The telephone-based intervention consists of a problem-solving telephone support educational intervention led by a trained interventionist. The intervention’s main objective is to reduce caregiver burden and depressive symptoms by teaching caregivers a creative and optimistic approach to solving caregiving related problems. The intervention will utilize the problem solving module and refer to additional information/tools on the Spanish RESCUE website (<http://www.cidrr8.research.va.gov/rescue-espanol/>). The information included in the intervention consists of: 1. Introduction, 2. Illustrative Example, 3. Individualized Practice Exercise, and 4. Summary.

The intervention is adapted from the intervention used in our previous pilot project and based on the work of Bakas et al.,[23] who conducted a successful 8-week telephone intervention which used support approach and a task skill-building kit (TASK). In this proposed project we will tailor our pilot intervention to be culturally relevant for a Puerto Rican population. The intervention was developed to reflect specific characteristics of the target population such as language, cultural values and norms, and degree of acculturation. To enhance the cultural relevance of the intervention, we will use findings from our previous projects and guidelines from authoritative sources [55] that recommend: 1) involving persons from the target population in all phases of the project (e.g., Advisory Consortium), 2) emphasizing themes that are valued by the PR culture (e.g., family, religion, self-reliance), 3) assuring that the language and wording of on-line information is low-literate and appropriate by enlisting services of certified translators and Spanish-speaking experts, and 4) conducting the intervention and assessments by hiring research staff members (i.e., interventionist, data collector) who are Hispanic, fluent in Spanish, and knowledgeable about the PR culture. Research consistently shows that matching interventions to the individual needs of participants is more effective in engaging adults and modifying behaviors than prescriptive approaches.,[16] Other studies underscore the benefits of interventions and programs that are tailored to a specific race/ethnic populations.[55]

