**Aim #1 - Hypothesis #1 (primary):** Stroke caregivers who receive the intervention will have less depressive symptoms at 1 and 12 weeks post-intervention compared to stroke caregivers in the standard care group. Our primary endpoint is the caregiver depressive score. The focus of the primary analysis will be to examine the effect of the intervention based on “intention to treat.” Data from all the participants will be part of the primary analyses regardless of actual number of completed sessions. As an exploratory study element, we will assess compliance and attempt to determine its effect on study results. For the primary analysis, the general linear mixed model for repeated measures will be used to model the follow-up depression times (1 and 12 weeks post-intervention), adjusted for baseline scores as fixed effects. Let  $y_{ij}$  be the depression score for person  $i$  at time  $j$ , then basic fixed effects model will be:

$$E(y_{ij}) = \beta_0 + \beta_1 \text{Baseline}_i + \beta_2 \text{Time}_{ij} + \beta_3 \text{Group}_i + \beta_4 \text{Group}_i * \text{Time}_{ij}$$

with covariates for baseline depression (Baseline), time (Time=0 for 1 week, 1 for 12 weeks post-intervention), and group (0 if active control, 1 if intervention). In order to control for possible chance sample imbalances resulting from randomization, the model will include covariates for baseline prognostic factors (e.g., discharge from hospital, community living center, or rehabilitation facility; caregivers’ relationship to Veteran; number of previous strokes among Veterans, etc.), deemed to have significant relationships with response and groupwise imbalances. Thus, analyses will be able to compare the groups on the measure of interest while controlling for these factors. The primary outcome of interest will be the immediate post-intervention effect at 1-week post-intervention with the 12-week post-intervention as a secondary outcome. This will be tested based on linear contrast  $\beta_3 + \beta_4$  at two-sided 0.05 level. All tests will be performed at the  $\alpha=0.05$  significance level. The correlation among observations from the same person will be accounted for through the inclusion of a random person effect into the mixed model analysis.

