**Aim #2 - Hypotheses #2 (secondary):** Stroke caregivers who receive the intervention will have superior outcomes (i.e., less burden, better problem solving skills, greater self-efficacy, and better HRQOL,) at 1 and 12 weeks post-intervention than caregivers in the standard care group. The analysis plan for Hypothesis 2 will closely follow the plan outlined above for Hypothesis 1 for each secondary outcome of interest.

**Aim #3 - Hypotheses #3 (secondary):** Veterans whose caregivers receive the intervention will have better functional abilities at 1 and 12 weeks post-intervention and less healthcare utilization at 12 weeks post-intervention measures compared to Veterans whose caregivers are in the standard care group. Since the score for the Stroke Impact Scale can be treated as a continuous, the analysis plan follows exactly as above in Hypothesis 1. Since the Veteran healthcare utilization measures are count data, the models will be a somewhat different. There will be no baseline covariates added to the model, as they are not applicable to the count measures. Analyses will be conducted for the period following baseline to 12 weeks post-intervention assessments. Generalized linear models for count data (such as Poisson or negative binomial regression models, depending on the presence or absence of over-dispersion) will be employed to determine the group effects on healthcare utilization. Log link functions will be employed on the count data to create the correct distributional data forms. As before, in order to control for possible sample imbalances resulting from randomization, all models will include covariates for prognostic factors deemed to have significant relationships with response and significant groupwise imbalances. Thus, analyses will be able to compare the groups on the measures of interest while controlling for these factors.

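### On the nominal schedule the second follow-up falls 13–15 weeks after the intervention, not at the stated 12, and its date can drift apart between the arms if sessions overrun

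*Combined protocol and SAP*

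**What the plan says.** Three groups of statements bear on the timing.

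- **Stated time points.** Section 5, Aim 1, concerns "stroke caregiver's depressive symptoms at 1 and 12 weeks post-intervention". The Design paragraph of section 6 lists "three assessment points (baseline, 1 week post-intervention and 12 weeks post-intervention". The primary model under Data Analysis, Aim #1, codes "time (Time=0 for 1 week, 1 for 12 weeks post-intervention". Fidelity Considerations uses the same 12-week name for the visit at which enactment is rated.
- **Schedule.** Under Data collection procedures, "post 1 will occur at approximately 9-10 weeks after enrollment", which for the intervention arm is equated with "1-2 weeks after completion of the intervention for participants in the intervention group". Then "post 2 will occur approximately 12-13 weeks after post-test 1". The same paragraph goes on to call that second call the 12-week assessment, and it has sessions and assessments arranged to suit the caregiver. Under Intervention, "Participants in the intervention group will participate in 8 weekly telephone sessions with an interventionist".
- **Utilisation period.** Under Data Analysis, Aim #3, for the count outcomes: "Analyses will be conducted for the period following baseline to 12 weeks post-intervention assessments". Poisson or negative binomial models are named. No offset for follow-up time is mentioned.

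No section states a tolerance around week 12 or ties post-test 2 directly to the end of the intervention.

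**The concern.** The schedule and the endpoint name cannot both be right as written. The 12–13 week interval is counted from post-test 1, whereas the endpoint is counted from the end of the intervention, and post-test 1 comes 1–2 weeks after that end. A durability result reported as a 12-week effect would describe a visit nominally held later.

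The second issue is the anchor. Any delay in post-test 1 carries over to post-test 2. In the intervention arm post-test 1 has two clocks, one from enrolment and one from completion, and they agree only if the eight sessions finish on time. Controls have only the enrolment clock. If sessions overrun and the completion clock governs, second visits move later in one arm only. For the questionnaire scores that is a difference in assessment time. For the utilisation counts it could be a difference in exposure, which a count model without an offset would read as a difference in rate.

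**Working it through.** **Inputs** (all from section 6): intervention of 8 weekly sessions, about 8 weeks; post-test 1 at 9–10 weeks from enrolment, or 1–2 weeks from completion; post-test 2 at 12–13 weeks from post-test 1; stated endpoint at 12 weeks from the end of the intervention.

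**1. Reproduce the plan's timing of post-test 1.** 8 + 1 = 9 and 8 + 2 = 10 weeks after enrolment. This matches, so the schedule implies completion at about week 8.

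**2. Post-test 2 from completion.** Earliest 1 + 12 = 13 weeks; latest 2 + 13 = 15 weeks. The excess over 12 is 1–3 weeks, or 1/12 = 8% to 3/12 = 25% of the post-intervention interval.

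**3. Post-test 2 from enrolment.** 9 + 12 = 21 to 10 + 13 = 23 weeks in both arms. A 12-week visit would be at 8 + 12 = 20 weeks. The excess is 1/20 = 5% to 3/20 = 15% of total follow-up.

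**4. Can the stated intervals reach week 12?** Post-test 1 would have to fall 12 − 12 = 0 weeks after completion, or 12 − 13 = −1, that is, one week before completion. Both lie outside 1–2 weeks.

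**5. Effect of delay.** The documents give no figure for delay or overrun, so *d* weeks is an assumption.

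- If post-test 1 alone is late by *d*, post-test 2 falls 13 + *d* to 15 + *d* weeks after completion; for *d* = 2, 15–17 weeks.
- If the sessions overrun by *d* and post-test 1 follows completion, intervention-arm post-test 2 falls 21 + *d* to 23 + *d* weeks after enrolment, with controls still at 21–23. Comparing midpoints, the ratio is (22 + *d*)/22:

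| Overrun *d* (assumed) | Intervention arm, weeks from enrolment | Controls | Ratio of midpoints |
|---|---|---|---|
| 0 | 21–23 | 21–23 | 22/22 = 1.00 |
| 1 | 22–24 | 21–23 | 23/22 = 1.05 |
| 2 | 23–25 | 21–23 | 24/22 = 1.09 |
| 4 | 25–27 | 21–23 | 26/22 = 1.18 |

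The ratio is one of counting time only if the utilisation count closes at the actual visit, and it takes *d* as the average overrun in the arm. Under the same condition, participants on schedule can differ by 23/21 = 1.10, without regard to arm.

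**6. Alternatives.** Anchoring post-test 2 at 12–13 weeks after completion puts it nominally at 8 + 12 = 20 to 8 + 13 = 21 weeks from enrolment, and 12 − 2 = 10 to 13 − 1 = 12 weeks after post-test 1. A pure enrolment clock at 20–21 weeks would see a caregiver who finishes *d* weeks late at 12 − *d* to 13 − *d* weeks after completion; for *d* = 2, 10–11 weeks.

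**The case against.** The best defence is that the labels are visit names taken from the lower end of each window: 1 week for 1–2, 12 weeks for 12–13. Both post-tests are described as approximate, so a given call may fall near week 12. A reader might infer that nobody is ever assessed at 12 weeks. The documents do not support that; only the nominal schedule excludes week 12. The defence does not remove the mismatch, though. No tolerance is given, and the whole nominal window lies on one side of 12.

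Four further points limit the concern.

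- **Bias.** The nominal shift is common to both arms, and the Aim #1 analysis text makes the later visit secondary. The shift itself does not bias the comparison. This stands in full.
- **Missed post-test 1.** A reader might infer that such a caregiver has no date for post-test 2. In fact the enrolment clock implies 21–23 weeks, nothing bars the call, and Handling of Missing Data does not require complete data on each subject. What remains is that the rule is implied and not written.
- **Drift.** The intervention workbook contains a calendar of agreed dates for sessions and for the post-test, and a procedure manual is cited that is not part of the documents. Either may restrain drift. The calendar entry is singular and may not cover post-test 2. Large delays cannot be inferred from the documents.
- **Utilisation.** A reader might take it that the call date closes the count. The Aim #3 text is ambiguous, and the Measures table has visit dates recorded, so the count can be cut at any chosen date.

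**Conclusion.** The concern holds as an inconsistency in a stated time point, together with an unprotected anchor. On the nominal schedule the second follow-up is 13–15 weeks after completion, 1–3 weeks beyond the label, and 21–23 weeks after enrolment against 20. This rests only on the plan's own intervals and, for the enrolment figures, on completion at about week 8, which the plan's timing of post-test 1 implies.

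Unequal timing between arms is conditional. It needs sessions to overrun and the completion clock to govern post-test 1. Unequal counting time needs, in addition, the utilisation count to close at the actual visit. Under those assumptions a 2-week average overrun gives about 9% more counting time in the intervention arm. That would raise that arm's expected counts with no true effect, working against the hypothesis of lower utilisation.

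The documents do not support a claim that the trial fails to measure durability or that its depression comparison is biased by the nominal shift. The sample size calculation does not depend on this point. The correction is worth making because it is nearly free. Also, under the printed coding (Time = 0 at 1 week), the one contrast written out, β3 + β4, is the group effect at this later visit, so its timing should be stated correctly.

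**What to change.** Reconcile Specific Aims, Design, Data collection procedures, Fidelity Considerations and the Aim #1 to #3 analysis text in one of two ways:

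1. **Relabel.** Keep the spacing and call the second follow-up about 13–15 weeks post-intervention (12–13 weeks after post-test 1) throughout.
2. **Re-anchor.** Count post-test 2 from the end of the intervention, using the planned end for controls, so that it falls at 12–13 weeks.

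The sponsor should choose, because each has a price. Relabelling leaves the chain to post-test 1 in place. Anchoring to actual completion keeps the endpoint's meaning but lets calendar time differ between arms when sessions overrun. A pure enrolment clock would equalise calendar time but would assess late finishers before week 12.

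With either choice:

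- state the visit window;
- say that post-test 2 is still attempted when post-test 1 is missed, dated from its nominal time;
- close the utilisation count at the same fixed number of weeks after baseline in both arms, using the dated records, whatever the date of the call.

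The cost is a scheduling sentence, one sentence on the counting period and matching endpoint wording. No calls, measures or participants are added.

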The intervention is described in detail in the table below. Based on prior studies, we anticipate that the calls will last between 45-60 minutes. However, the length of the calls will vary depending on the needs of the caregivers. We will document the length of the calls and adjust for this dose-response effect in the analysis. 10% of participants will have an intervention session recorded for quality assurance and training purpose. No session will be recorded without first informing the participant and obtaining their oral consent for the recording (see fidelity considerations below).

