**Fidelity Considerations:** We will make special effort to enhance, maintain and track treatment fidelity. We will use recommendations of Borelli, et al.,[63] and Burgio et al.[64] as our guide. We will adapt the standardized manuals and protocols that were used in our pilot project. This manual will provide step-by-step guidelines on recruiting/enrolling participants, implementing the informed consent process, in conducting the intervention and implementing the data collection procedures. We will provide extensive training to all of our team members. [name] will periodically observe the interventionists conducting the telephone intervention. We will have monthly meetings with the interventionists to discuss implementation of the intervention and discuss protocol issues. To monitor the delivery of the intervention we will audio-tape (digitally record) 10% of the telephone sessions throughout the duration of the project with oral consent from the study participants (Consent will be obtained orally because we are requesting a HIPAA Waiver and Waiver of Documentation for Informed Consent). We will also record the number of minutes spent with each participant and to keep detailed notes of any deviations from our study protocol. The PI and data collector will review these audiotapes and evaluate adherence to study protocols, noting all deviations on a form. Feedback will be provided as needed.

Similar to Bakas, et al.,[23] we will evaluate "enactment" by asking caregivers (in intervention group) after completion of the study (at 12 week post-intervention time-point) to rate the amount of information and contact they received during the 8-session intervention, how much they used the skill-building strategies and the RESCUE website, how helpful the intervention was and whether their problems were resolved.

**Measures:** We carefully chose measures that had been translated into Spanish, used in previous research studies, had good psychometric properties, were easy to administer, and were relatively short in length to reduce participant burden. Most of the measures selected were tools that our team members had used previously in other studies. In the table below, we describe the measures we will use for screening caregivers to determine their study eligibility as well as the measures related to testing hypotheses 1-3. Our other measures are described in later sections. See proposed instruments below.

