To further protect study participants from any risks, our intervention will be conducted by trained interventionist(s) with experience in conducting mental health assessments and counseling. We will hire an interventionist knowledgeable about caring for individuals and family members who are in stressful situations, such as involved in caregiving. Training of the interventionist(s) will include independent readings, didactic instruction, and role-playing. Throughout the project, the investigators will observe/listen to the interventionist(s) conducting the interventions and evaluate his or her fidelity to the protocol, decision-making skills, and how they handle the caregivers' problems and stress. If needed, select intervention sessions will be audio-recorded to facilitate fidelity checks if the participant agrees. Feedback and additional training, if needed, will be provided. The interventionists will make every effort to minimize the potential risks by maintaining a professional, pleasant manner and allowing caregivers to ask questions and discuss feelings. In the intervention arm, the interventionist(s) will assist the caregivers in solving their problems using the problem-solving approach. The interventionist(s) will not provide advice, but rather will advise caregivers to access information on the Caregiver Family Alliance website ([www.caregiver.org](http://www.caregiver.org)) for managing problems. In the event that the interventionist(s) assess that caregivers in any arm of the study are experiencing unmanageable, but not severe stress or depression, they will advise the caregivers to call their assigned VA social workers and primary care clinicians (MD, ARNP, PA). The interventionist(s) will also give the caregivers the phone number of the VA Caregiver Support Line. If the interventionist(s) assess that the caregivers are in severe stress, depression or crisis, or have serious changes in their health, the interventionist(s) will call either one of the study physician Co-investigators or the caregivers' VA primary care social workers and VA primary care healthcare providers (MD, ARNP, PA) immediately or 911 depending on the circumstances. If any abuse or neglect is suspected, study personnel will follow established procedures by oversight agencies including VHA as directed in the VA Handbook 1050.01 to contact the Office of Inspector General, Office of Investigation, as well as the IRB and the state of Abuse Hotline. We will train all study personnel to protect against all foreseeable risks. Team members also will be trained in monitoring and reporting adverse events.

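### The data collector declared blinded for the post-test calls is also given tape review and the intervention-only Enactment tool, and nothing separates or orders these duties

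*Combined protocol and SAP*

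**What the plan says.** All references are to section 6, Research Plan, of the combined protocol and SAP unless stated.

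- **Blinding.** Data collection procedures: "The data collector, who will be blinded to the group assignment of the caregivers, will telephone the caregivers to obtain the post-test assessments".
- **Tape review.** Fidelity Considerations: "The PI and data collector will review these audiotapes and evaluate adherence to study protocols, noting all deviations on a form". The Intervention section gives telephone sessions, eight of them weekly, to the intervention group only.
- **Enactment.** The blinding statement comes shortly after a sentence that has the data collector put the Enactment questions at the 12-week post-test. Fidelity Considerations and the Measures table both restrict that tool to intervention caregivers.
- **How much is taped.** The Intervention section says "10% of participants will have an intervention session recorded for quality assurance and training purpose". Fidelity Considerations says "we will audio-tape (digitally record) 10% of the telephone sessions throughout the duration of the project".
- **Primary time-point.** Aim #1, Hypothesis #1: "The primary outcome of interest will be the immediate post-intervention effect at 1-week post-intervention with the 12-week post-intervention as a secondary outcome".

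Data collection procedures introduces a single data collector, who also makes the baseline call. The plural appears later in that section, in a sentence on record abstraction, and again under Handling of Missing Data. Neither place divides the duties.

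**The concern.** A person who listens to a caregiver's session tape, or who knows that a caregiver is due the Enactment questions, knows that caregiver's arm. If the same person then reads out the CES-D by telephone and records the answers, the assessment is not blinded for that caregiver. Caregivers cannot be blinded here, so the interviewer's blinding is the safeguard left at the point of measurement, and it is one that the protocol chose to claim. At stake is whether a report of this trial can truthfully describe its outcome assessment as blinded, above all for the primary 1-week CES-D.

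**Working it through.** The plan gives no figure for this point, so there is none to reproduce. The check has two parts.

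**1. Which duty can reach which assessment**

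| Duty of the data collector | Reveals the arm? | Can precede the 1-week CES-D? | Can precede the 12-week scales? | Order stated? |
|---|---|---|---|---|
| Tape review | Yes, if the caregiver is recognisable | Yes | Yes | No |
| Enactment | Yes, to whoever must know to ask it | No, it is a 12-week task | Yes, if asked or flagged first | Visit only, not order within it |

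Early review of tapes is plausible. Sessions are weekly, so session 1 falls 7 weeks before session 8, and post-test 1 follows completion by 1 to 2 weeks. If completion means session 8, the gap between a recording and post-test 1 runs from 1–2 weeks (session 8) to 7 + 1 = 8 and 7 + 2 = 9 weeks (session 1). Fidelity Considerations provides for monthly meetings with the interventionists and feedback as needed, and such feedback works best when review is prompt. Subject codes (Data Privacy, Confidentiality, and Safety) do not disguise a voice already heard at the baseline call.

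For Enactment, order within the call is not the whole matter. If the caller's paperwork shows beforehand who is to receive it, the arm is known from the start of the call.

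**2. How many caregivers tape review could expose before the 1-week CES-D**

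Inputs: 227 caregivers (Sample); 8 sessions (Intervention); 10% taped (two statements, above). Assumption: 1:1 allocation, which the plan does not state as a ratio.

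- Intervention arm: 227 / 2 = 113.5 caregivers.
- Review always after the post-tests: 0 exposed.
- 10% of participants, read as intervention participants: 0.10 × 113.5 = 11.35, about 11 caregivers, 10% of the arm.
- 10% of participants, read as all 227: 0.10 × 227 = 22.7, about 23 caregivers. Only the intervention arm has sessions, so this is 22.7 / 113.5 = 20% of that arm.
- 10% of sessions: 113.5 × 8 = 908 sessions; 0.10 × 908 = 90.8, about 91 tapes. If all eight sessions of the same caregivers are taped, 90.8 / 8 = 11.35 caregivers (10%). Any wider spread touches more. The sampling method is not stated.

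These are counts of taped caregivers. The number exposed is smaller unless the outcome caller hears each of those tapes before post-test 1.

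**The case against.** **Several people may share the role.** The title is used loosely, also for chart abstraction, and the plural appears twice. The documents therefore allow the tape reviewer and the outcome caller to be different people, and the procedure manual, which is not among the documents, may say so. This stands as a reason not to claim that blinding will fail. It does not rescue the text, which gives the duties to one named role and divides them nowhere.

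**Enactment may already come last.** Fidelity Considerations places it once the study is finished, and the data collection text presents it as an addition to the assessment. Only the latter names the data collector as the one who asks. This is fair, but the finishing point is defined as the same 12-week time-point, so order within the call stays open.

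**Blinding is only partial protection here.** The scales are self-reported with fixed responses, callers are trained, and caregivers know their arm and may disclose it on any call. All of this limits the possible harm, and no fix prevents disclosure by the caregiver.

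A reader might infer more than the documents support:

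- *That most of the arm is exposed.* Random sampling of 10% of sessions would give 1 − 0.9^8 = 57% of the arm at least one tape, and one tape per caregiver would give 90.8 / 113.5 = 80%. Both need a sampling pattern, and an outcome caller who hears every tape before post-test 1. The plan states neither.
- *That the Used Resources Survey is a further route.* The plan does not say who asks it, and the Standard Care Group section puts that group's question at the end of the study. That the blinded caller asks it, and is unmasked by the answers, is inference.
- *That the primary result is biased.* Nothing in the documents yields a bias in CES-D points.

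**Conclusion.** Wrong as written, of moderate to low severity. The protocol states that the outcome assessor is blinded and then assigns the same role duties that disclose the arm, without separating or ordering them.

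For the primary 1-week CES-D, tape review is the only one of these routes. Exposure runs from none to about 10% or 20% of the intervention arm under the participant-based taping rate, and may be higher under the session-based rate. This rests on 1:1 allocation of 227, on recognisable tapes, and on the outcome caller hearing them first. Enactment can affect only the secondary 12-week scales, and has no effect if those are complete before the arm is revealed.

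The discrepancy between the taping rates is a separate matter. It enters here only because it sets the range.

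**What to change.** Two short additions to the text:

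1. **Fidelity Considerations.** State that no one who makes a caregiver's outcome calls reviews that caregiver's tapes until post-test 2 is complete. Until then the PI, already a named reviewer, or a collector who does not call that caregiver reviews them. Section 7 already provides that "Throughout the project, the investigators will observe/listen to the interventionist(s) conducting the interventions and evaluate his or her fidelity to the protocol".
2. **Data collection procedures.** State that at 12 weeks all outcome scales are completed and locked before the caller learns the arm and before Enactment is given. The instruction on who receives Enactment should not be visible to the caller until then.

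**Cost.** If the PI and the collector now both hear each tape, some tapes lose their second listener and the PI's time is unchanged. If they now split tapes equally (an assumption) and the PI takes them all, the PI's added time is half the tapes at the stated call length ("Based on prior studies, we anticipate that the calls will last between 45-60 minutes"):

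- 11.35 / 2 × 0.75 to 1 h = about 4 to 6 hours;
- 22.7 / 2 × 0.75 to 1 h = about 9 to 11 hours;
- 90.8 / 2 × 0.75 to 1 h = about 34 to 45 hours.

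These are totals over the whole trial. The second addition costs only a change to the call form.

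**Minor note, not needed for the point.** The Aim #5 section also gives the data collector the interviews with 8–12 intervention caregivers, without saying that they follow post-test 2. Someone who does not make that caregiver's outcome calls could conduct them, which avoids delaying the interviews.
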